2. SUS CREINCIAS ACERCA DE DIENTES DE LOS NIÑOS Y CUIDADO DENTAL

Los padres tienen diferentes creencias acerca de obtener cuidado dental de sus niños/as. Por favor diganos cuanto está usted de acuerdo o desacuerdo con las siguientes declaraciones al circular el número que mejor se ajuste a su respuesta.

	Totalmente de acuerdo	De acuerdo	Ni de acuerdo ni en desacuerdo	Desacuerdo	En total desacuerdo
2a. Eventualmente la mayoría de los niños/as desarrollan caries dentales	1	2	3	4	5
2b. Las caries en los dientes de leche no importan ya que de todos modos se caen	1	2	3	4	5
2c. No sé cómo llevar a mi niño/a al dentista para que le arreglen sus caries.	1	2	3	4	5
2d. Si me llevé a mi hijo al dentista, no haría ninguna diferencia si o no él/ella desarrolle caries.	1	2	3	4	5
2e. Yo intentaré llevar a mi niño/a al dentista al menos una vez al año.	1	2	3	4	5
2f. No puedo hacer que mi niño/a vaya al dentista.	1	2	3	4	5
2g. El dentista es la mejor persona para prevenir las caries de mi niño/a.	1	2	3	4	5
2h. No sé cómo cepillarle los dientes apropiadamente a mi niño/a.	1	2	3	4	5
2i. Si le ayudo a mi niño/a cepillarse todos los días, no hará ninguna diferencia si o no él/ella desarrolle caries	1	2	3	4	5
2j. Intento cepillarle los dientes a mi niño/a dos veces al día.	1	2	3	4	5
2k. No puedo hacer que mi niño/a cepille sus dientes dos veces al día.	1	2	3	4	5

Sitio del estudio: _____ # de identificación: _____

Cuestionario del cuidador Último seguimiento

3. SUS PENSAMIENTOS ACERCA DE LLEVAR A SU NIÑO/A AL DENTISTA

3a – 3b. Las siguientes preguntas son acerca de lo que otros piensan acerca de llevar a su niño/a al dentista para cuidado preventivo y tratamiento dental. *Por favor diganos como se siente haciendo un círculo en el número que se ajuste a su respuesta.*

Personas importantes para mí ...	Completamente en desacuerdo	Desacuerdo	Neutral	De acuerdo	Totalmente de acuerdo
3a1. Piensan que debería llevar a mi niño/a al menos una vez al año.	1	2	3	4	5
3a2. Aprobarían si tuviera que llevar a mi niño/a al dentista al menos una vez al año.	1	2	3	4	5
3a3. Llevan a su niño/a al dentista al menos una vez al año.	1	2	3	4	5
<hr/>					
3b1. Piensan que cuando se encuentre un problema en un diente debería llevar a mi niño/a al dentista	1	2	3	4	5
3b2. Aprobarían que llevara a mi niño/a al dentista cuando se encuentre un problema en el diente	1	2	3	4	5
3b3. Llevan a su niño/a al dentista cuando se encuentre un problema en un diente	1	2	3	4	5

Sitio del estudio: _____ # de identificación: _____

Cuestionario del cuidador Ultimo seguimiento

3c. Algunas veces los padres atrasan el cuidado dental de su niño/a cuando otras cosas se presentan en el camino. ¿Qué probabilidades hay que lleve a su niño/a al dentista cuando lo siguiente pase? Por favor circule el número que mejor se adapte a su respuesta.

Que probabilidades hay que usted lleve a su niño/a al dentista cuando usted está ...	Muy Probable	Moderadamente probablemente	Possiblemente	No hay probabilidad
3c1. Bajo mucho estrés	1	2	3	4
3c2. Deprimida	1	2	3	4
3c3. Ansiosa	1	2	3	4
3c4. Sintiéndose que no tiene el tiempo (muy ocupado)	1	2	3	4
3c5. Cansada	1	2	3	4
3c6. Preocupada por otras cosas en su vida	1	2	3	4
3c7. Molesta por su niño/a llorando	1	2	3	4
3c8. Molesta porque su niño/a no se está quieto para que el dentista lo examine	1	2	3	4
3c9. Su niño/a le dijo que no quiere ir al dentista	1	2	3	4

Sitio del estudio: _____ # de identificación: _____

Cuestionario del cuidador Último seguimiento

4. EL COMPORTAMIENTO DEL CUIDADO DENTAL DE SU NIÑO/A*Por favor haga un círculo en la letra que mejor se adapte a su respuesta acerca de su niño/a.***4.1 Durante una semana *ideal*, ¿cuán frecuente se cepilla los dientes su niño/a?**

- a) No se cepilla sus dientes
- b) Menos de una vez a la semana
- c) Una o dos veces a la semana
- d) Un día si un día no
- e) Casi todos los días
- f) Una vez al día
- g) Dos veces al día
- h) Mas de 2 veces al día
- i) No se

4.2 ¿Desde el inicio del año escolar, tuvo su niño/a algún tipo de cobertura dental? Tal como plan privado, plan preferencial (como una membresía de organización de mantenimiento de salud (HMO por sus siglas en Ingles) o plan de gobierno (como Medicaid).

- a) Si → Por favor responda la pregunta 4.2a
- b) No
- c) No se

4.2a ¿Estuvo su niño/a asegurado por Medicaid o el programa de seguro de salud de niños/as (S-CHIP por sus siglas en Ingles)?

- a) Si
- b) No
- c) No se

4.3 ¿Hay un lugar al que su niño/a usualmente va cuando necesita tratamiento para su problemas dental, como caries o dolor de dientes?

- a) Si → Por favor responda la pregunta 4.3a
- b) No
- c) No se

Sitio del estudio: _____ # de identificación: _____

Cuestionario del cuidador Último seguimiento

4.3a Si su respuesta es SI, es este un lugar:

- a) Oficina del dentista
- b) Departamento de emergencia
- c) Hospital
- d) Clínica
- e) Otro, por favor escriba aquí _____

4.4 Algunas veces personas tienen problemas en obtener todo el tratamiento dental que necesitan. Desde el inicio del año escolar, ¿hubo alguna vez que su niño/a necesito cuidado dental pero fue retrasado o no lo recibió?

a) Si → Por favor responda la pregunta 4.4a

b) No

c) No se

Por favor sáltense la pregunta 4.5

4.4a Despues que un problema fue encontrado por un proveedor dental, ¿qué tipo de tratamiento fue atrasado o no fue recibido? Por favor haga un círculo en todas las que apliquen.

- a) Rellenos
- b) Extracciones (sacarse un diente)
- c) Corona (casquillo de metal)
- d) Terapia de pulpa (endodoncia en diente de leche)
- e) Enfermedad en las encillas
- f) Otro, por favor especifique
- g) No me acuerdo

4.5 ¿Visitó su niño/a al dentista después de la evaluación dental en la escuela?

a) Si → Vaya a la pregunta 5A

b) No → Vaya a la pregunta 5B

5A. SUS PENSAMIENTOS ACERCA DEL ESTUDIO

Si usted contestó SI a la Pregunta 4.5 (su niño visitó al dentista), por favor responda a las siguientes preguntas:

5.1 ¿Cuál es el nombre de la clínica dental/dentista donde usted llevó a su niño/a?

5.2 ¿Qué mes después de la evaluación dental llevo a su niño/a al dentista?

5.3 ¿Llevó la carta de referencia (de la evaluación visual dental de la escuela) con usted al dentista?

- a) Si
- b) No

5.4 ¿Completo su niño/a el tratamiento dental necesario?

- a) Si

Si es SI, ¿cuántas visitas fueron necesarias para completar el tratamiento dental de su niño/a?

- b) No, pero mi niño/a tiene una cita de seguimiento

Si NO, ¿cuándo es la cita de seguimiento? _____

- c) No

Si NO, ¿porque su niño/a no completo el tratamiento dental? _____

- d) No se

Por favor VAYA a la Pregunta 5.5

Sitio del estudio: _____ # de identificación: _____

Cuestionario del cuidador Último seguimiento

5.5 ¿Hubieron algunos puntos anteriormente que le ayudaron a usted a llevar a su niño al dentista?*Por favor circule todos los que apliquen.*

- a) La carta de referencia
- b) Información acerca de mitos y hechos acerca de la salud dental de los niños/as
- c) Consejos útiles para obtener cuidado dental para su niño/a
- d) Información en cómo hacer una cita dental para su niño/a
- e) Conocer acerca de los dentistas en su área
- f) El alcance individual
- g) No se

5.6 ¿Encontró que la carta de referencia fue fácil de entender?

- a) Si
- b) No

5.7 ¿En cuál grupo de estudio piensa usted que estuvo usted y su niño?

- a) En la carta estándar
- b) En la carta de mejoramiento
- c) En la carta de mejoramiento con materiales
- d) No se

¡GRACIAS!

Sitio del estudio: _____ # de identificación: _____

Cuestionario del cuidador Ultimo seguimiento

5.B SUS PENSAMIENTOS ACERCA DEL ESTUDIO

*Si usted contestó **NO** a la Pregunta 4.5 (su niño/a no visitó al dentista), por favor responda a las siguientes preguntas:*

5.1 Las siguientes preguntas son acerca de llevar a su niño/a al dentista. Por favor circule el número que es más apropiado para su respuesta

	Completamente en desacuerdo	Desacuerdo	Neutral	De acuerdo	Totalmente de acuerdo
5.1a Yo quiero llevar a mi niño/a al dentista	1	2	3	4	5
5.1b Yo planeo llevar a mi niño/a al dentista	1	2	3	4	5

5.2 Porque su niño/a NO ha podido ir a visitar al dentista desde la evaluación visual en la escuela? Aquí hay algunas razones de otros padres – por favor circule todas las que aplican.

- a) Cuesta mucho
- b) Mi niño no tiene seguro dental o Medicaid
- c) Mi familia tiene problemas con nuestro plan de cuidado de salud
- d) No puedo encontrar un dentista que acepte el seguro de mi niño/a
- e) No hay dentistas disponibles en mi área / tengo problema de transporte
- f) Es difícil poder obtener horarios convenientes para las citas / mi niño/a no puede obtener una cita
- g) El dentista no sabe cómo tratar o proveer cuidado a mi niño/a
- h) Yo estaba insatisfecho con el dentista
- i) No sabía a dónde llevar a mi niño/a para tratamiento
- j) Mi niño/a rehúsa a ir
- k) El tratamiento de mi niño/a es continuo (se está llevando a cabo)
- l) Otra, por favor especifique _____

Sitio del estudio: _____ # de identificación: _____

Cuestionario del cuidador Último seguimiento

5.3 ¿Hubieron algunos puntos anteriormente que le habría ayudado a usted a llevar a su niño al dentista? *Por favor circule todos los que apliquen.*

- a) La carta de referencia
- b) Información acerca de mitos y hechos acerca de la salud dental de los niños/as
- b) Consejos útiles para obtener cuidado dental para su niño/a
- c) Información en cómo hacer una cita dental para su niño/a
- d) Conocer acerca de los dentistas en su área
- e) El alcance individual
- f) No se

5.4 ¿Encontró que la carta de referencia fue fácil de entender?

- a) Si
- b) No

5.5 ¿En cuál grupo de estudio piensa usted que estuvo usted y su niño?

- a) En la carta estándar
- b) En la carta de mejoramiento
- c) En la carta de mejoramiento con materiales
- d) No se

¡GRACIAS!

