3.2.1 Primary Outcome Measures

The primary outcome will be receipt of dental care based on a change determined by clinical examination between baseline and follow-up at study exit (7 months after baseline). Please see MOP Section 5.2 for details of dental exam and criteria.

In addition, other proximal surrogate outcomes from the caregiver questionnaire will also be assessed. These questions include: whether the child visited the dentist after the dental screening, the name of the dentist/dental clinic, whether an appointment was made or not, whether the child completed the needed dental treatment, the number of visits that were made to complete dental treatment, and if they did not complete the treatment the reasons why they did not complete the treatment.

Examiner Training and Calibration: Exams will be conducted in a portable dental chair in the schools by a trained/calibrated examiner. [name] will train/calibrate the examiners in the ICDAS protocol in a 4-day central training session. Detailed caries assessment and examiner training, calibration and reproducibility protocols are in the MOP (Section 5.2). Examiners will not utilize dental radiographs. At follow-up, the examiner will not have access to the results of the first examination to avoid detection bias.

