4.1 During an ideal week, how often does your child brush his/her teeth?

- a) Doesn't brush his/herteeth
- b) Less than once a week
- c) Once or twice a week
- d) About every other day
- e) Almost every day
- f) Once a day
- g) Twice a day
- h) More than twice a day
- i) Don't know

4.2 Since the start of this school year, did your child have any kind of dental coverage, such as a private plan, preferred plan (like an HMO), or government plan (like Medicaid)?

- a) Yes → Please answer Question 4.2a
- b) No
- c) Don't know

4.2a Was your child insured by Medicaid or the State Children's Health Insurance Program (S-CHIP)?

- a) Yes
- b) No
- c) Don't know

4.3 Is there a place your child usually goes when he/she needs treatment for a dental problem, like a cavity or tooth pain?

- a) Yes → Please answer Question 4.3a
- b) No
- c) Don't know

Study Site: _____ ID#: _____

Caregiver Questionnaire-Final Follow-up

4.3a If you answered YES, is this place a:

- a) Dentist's office
- b) Emergency department
- c) Hospital
- d) Clinic
- e) Other, please specify _____

4.4 Sometimes people have trouble getting all the dental treatment they need. Since the start of this school year, was there any time when your child needed dental care but it was delayed or not received?

- a) Yes → Please answer Question 4.4a
- b) No
- c) Don't know } Please skip to Question 4.5

4.4a What type of treatment was delayed or not received after a problem had been found by a dental provider? Please circle all that apply.

- a) Filling
- b) Extraction [having a tooth pulled]
- c) Crown / metal cap
- d) Pulp therapy [baby root canal]
- e) Gum disease
- f) Other, please specify _____
- g) Don't remember

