4.5 Did your child visit the dentist after the school dental screening?

- a) Yes → Go to Question 5A
- b) No → Go to Question 5B

Study Site: _____ ID#: _____

Caregiver Questionnaire-Final Follow-up

5A. YOUR THOUGHTS ABOUT THE STUDY

If you answered YES to Question 4.5 (your child visited the dentist), please answer the following questions:

5.1. What is the name of the dental clinic / dentist where you took your child?

5.2. What month after the dental screening did you take your child to the dentist?

5.3. Did you take the referral letter (from the school dental screening) with you to the dentist?

- a) Yes
- b) No

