8.7a Si su respuesta es **SI**, Es este un lugar:

- a) oficina del dentista
- b) departamento de emergencia
- c) hospital
- d) clínica
- e) otro, por favor escriba aquí _____

8.8 Algunas veces personas tienen problemas en obtener todo el tratamiento dental que necesitan. Durante los *últimos 12 meses*, ¿hubo alguna vez que su niño/a necesito cuidado dental pero fue retrasado o no lo recibió?

- a) Si → Por favor responda las preguntas 8.8a y 8.8b

- b) No
- c) No se

Por Favor, Saltase al Número 8.9

8.8a Después que un problema fue encontrado por un proveedor dental, ¿qué tipo de tratamiento fue atrasado o no fue recibido? *Por favor haga un círculo en todas las que apliquen.*

- a) rellenos
- b) extracciones (sacarse un diente)
- c) corona (casquillo de metal)
- d) terapia de pulpa (endodoncia en diente de leche)
- e) enfermedad en las encillas
- f) otro, por favor especifique
- g) no me acuerdo

sitio del estudio _____ # de identificación _____

Cuestionario del cuidador -Referencia

8.8b ¿Porque su niño no obtuvo todo el cuidado dental que necesitaba? Aquí hay algunas razones comunes--- *por favor haga un círculo en las que apliquen.*

- a) Cuesta mucho
- b) Mi niño no tiene seguro dental o Medicaid
- c) Mi familia tiene problemas con nuestro plan de cuidado de salud
- d) No puedo encontrar un dentista que acepte el seguro de mi niño/a
- e) No hay dentistas disponibles en mi área / tengo problema de transporte
- f) Es difícil poder obtener horarios convenientes para las citas / mi niño/a no puede obtener una cita
- g) El dentista no sabe cómo tratar o proveer cuidado a mi niño/a
- h) Yo estaba insatisfecho con el dentista
- i) No sabía a dónde llevar a mi niño/a para tratamiento
- j) Mi niño/a rehúsa a ir
- k) El tratamiento de mi niño/a es continuo (se está llevando a cabo)
- l) Mi niño necesita una referencia y no podemos obtener una
- m) Otra, por favor especifique _____

8.9 ¿Durante los *últimos 12* meses, usted, un doctor o dentista pensaron que su niño/a necesitaba ver a un especialista dental (por ejemplo, un dentista pediatra)?

- a) Si →Por favor responda la pregunta 8.9a
- b) No
- c) No se

8.9a ¿Durante los *últimos 12* meses, cuantos problemas - si alguno- tuvo para obtener el cuidado del especialista que su niño/a necesitaba?

- a) un problema grande
- b) un problema pequeño
- c) no hubo ningún problema
- d) no se

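### The Spanish final caregiver questionnaire tells those answering No or Don't know at 4.4 to skip question 4.5, where the English form sends them to it, so reported dental visits may be missing in a non-random way

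*Combined protocol and SAP*

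**What the plan says.** Section 3.2.1 of the protocol takes the primary outcome from the dental exam: "receipt of dental care based on a change determined by clinical examination". It then lists caregiver-reported surrogate outcomes to be assessed as well. The first is "whether the child visited the dentist after the dental screening"; the clinic name, completion of treatment and number of visits are among the others.

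At the final follow-up the visit is asked in item 4.5 of the caregiver questionnaire: "4.5 Did your child visit the dentist after the school dental screening" in English and "Visitó su niño/a al dentista después de la evaluación dental en la escuela" in Spanish. A Yes routes to section 5A and a No to section 5B.

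The item before it, 4.4, asks in Spanish "hubo alguna vez que su niño/a necesito cuidado dental pero fue retrasado o no lo recibió", that is, whether needed care was delayed or not received. Those answering Yes are sent to 4.4a (type of care). For No and Don't know the two language versions differ:

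- English: "Please skip to Question 4.5"
- Spanish: "Por favor sáltense la pregunta 4.5"

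The equivalent jump in the Spanish baseline questionnaire, at item 8.8, is worded as a jump to a destination: "Por Favor, Saltase al Número 8.9".

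**The concern.** The English wording makes the caregiver pass over 4.4a and answer 4.5. The Spanish wording lacks the 'to' and makes 4.5 the question to be left out. Section 16.2 says the questionnaires are completed on paper by the caregivers, so no software corrects the route.

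Three things are at stake among Spanish-form families:

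- the answer to 4.5 itself, a named surrogate outcome;
- the section 5A details (clinic, month, completion, number of visits), which are reached through a Yes at 4.5;
- the section 5B items, reached through a No: the reasons for not visiting and the two items that form the 7-month behavioral intention score. Section 3.2.2 makes change in that score a secondary outcome.

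The blanks would not fall at random. Whether 4.5 is asked depends on the answer to 4.4, and that answer may be related to whether the child was seen.

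**Working it through.** **1. Is it an error on this form or a house style?** The Spanish baseline form (8.8 to 8.9) and the Spanish 2-week form (1.1 to 1.5 or 1.6) both word their jumps as 'skip to'. Only the 4.4 instruction on the final form drops the 'to'. It is therefore a slip on one form, and the two final forms give opposite instructions.

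**2. Who is told to omit 4.5?** Caregivers on the Spanish final form who answer No or Don't know to 4.4. Those answering Yes go through 4.4a and reach 4.5 normally. English-form caregivers are unaffected.

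**3. What would this do to a reported visit rate?** The plan gives no figure to reproduce. Within Spanish-form families, let

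- v = true visit rate;
- a = probability of No or Don't know at 4.4 among visitors;
- b = the same among non-visitors;
- c = share who obey the instruction literally.

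Then

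- observed rate = v(1 − ac) / [v(1 − ac) + (1 − v)(1 − bc)]
- share missing = 1 − [v(1 − ac) + (1 − v)(1 − bc)]

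Only a value for v can be borrowed from the documents: 37%, the section 12.2 planning rate for the CSM letter alone. The values of a, b and c are assumptions, chosen only to show how the sign behaves.

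| a, b | c = 25% | c = 50% | c = 100% |
|---|---|---|---|
| 0.8, 0.5 | 34.9% (15% missing) | 32.0% (31%) | 19.0% (61%) |
| 0.6, 0.6 | 37.0% (15%) | 37.0% (30%) | 37.0% (60%) |
| 0.5, 0.8 | 39.1% (17%) | 42.3% (34%) | 59.5% (69%) |

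Worked cell, a = 0.8, b = 0.5, c = 50%: visitors retained 0.37 × (1 − 0.40) = 0.222; non-visitors retained 0.63 × (1 − 0.25) = 0.4725; observed rate 0.222 / 0.6945 = 32.0%; missing 1 − 0.6945 = 31%.

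Worked cell, a = 0.5, b = 0.8, c = 100%: 0.37 × 0.5 = 0.185; 0.63 × 0.2 = 0.126; observed rate 0.185 / 0.311 = 59.5%; missing 69%.

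The rate is understated when a > b, unbiased when a = b, and overstated when a < b. The table shows that the sign turns on an unknown; it does not estimate an effect in this trial.

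**4. And a comparison of arms?** The observed odds equal v/(1 − v) × (1 − ac)/(1 − bc). If a, b and c are the same in two arms, the second factor cancels and the odds ratio within Spanish-form families is unchanged. Differences and ratios of rates do change. If a, b or c differ by arm, the odds ratio can move too, in either direction.

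**5. Does the plan deal with such blanks?** Section 12.4 treats missing questionnaire responses under the IPQ-RD and intention analyses. It counts data as missing completely at random only if missingness does not depend on other item responses. A blank produced by the answer to 4.4 fails that definition. Section 12.4 states no rule for reported visits.

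**The case against.** A reader might infer more than this: that caregivers who report no delay are mostly those whose child was treated, so that visits are lost mainly from families who received care and the results understate both the visit rate and the benefit of the new letters. The documents do not support that. Section 2.1 says most low-income caregivers respond only to pain or visible decay. A non-visiting caregiver who saw no need can answer No to 4.4, and a visitor who waited months can answer Yes. Don't know triggers the skip as well. With a = 0.4, b = 0.7 and full compliance, true rates of 19% and 57% would be observed as 31.9% and 72.6%, overstating both the rates and the difference (41 points instead of 38). The direction is open.

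Other points against the concern also carry weight:

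- **Compliance.** Item 4.5 is printed after 4.4a with its own arrows to 5A and 5B, and some caregivers will answer it regardless.
- **Recovery.** The 5A and 5B headings state in words whether the child visited, so a caregiver can choose the right section and visit status can often be read from the one completed.
- **Existing checks.** Section 14.2 provides double entry, checks for missing data and clarification of unclear fields with the caregiver. Section 16.4 adds review by outreach workers, coordinators and the data team. These may catch some blanks, although a blank that follows a printed skip can pass as legitimate.
- **Planned inference.** Section 12.4 specifies no analysis of reported visits and none of their agreement with the exam.
- **Text extraction.** The reading turns on one short word in text taken from a PDF. Nothing shows that it was lost in extraction, and it survives in the 2-week form, but the printed form should be checked.

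These points limit the consequence. They do not remove the contradiction between the two language versions.

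**Conclusion.** The point stands as a limited instrument error. As written, the Spanish final form tells some caregivers to omit a surrogate outcome named in section 3.2.1 and breaks the printed route to sections 5A and 5B, including the 7-month intention items. Among Spanish-form families, missingness then depends on the answer to 4.4 and could bias reported-visit results.

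Neither the sign nor the size of any bias can be stated, because the documents do not give the number of Spanish forms, the share who comply literally, or the relation between 4.4 and visiting. A demonstrated bias in arm effects should not be claimed. The primary outcome comes from the exam and is untouched.

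The conclusion assumes that the printed form matches the text in Appendix C and that at least some caregivers follow it literally.

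**What to change.** - **Form.** Check the printed Spanish final questionnaire. If it matches Appendix C, change the instruction at 4.4 to 'Pase a la pregunta 4.5' on any copy still to be used. The second recruitment year in section 5.3 names only Ohio districts, so forms already returned may be the larger part of the problem.
- **Returned forms.** Do not score a blank 4.5 as no visit. Recover the answer from whichever of 5A or 5B was completed, or through the section 14.2 clarification process, and record which source was used.
- **Reporting.** Give the number of Spanish final forms and how many lack 4.5, by arm. Present caregiver-reported visit results with and without the Spanish forms still missing 4.5.

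The cost is one corrected line, review of the revised form by the IRB, and a short data-cleaning rule. No extra visits are needed; the added work is checking the returned Spanish forms and clarifying blanks.
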